9.4.8.2 Glucocorticoid Treatment of Elevated Hepatic Transaminases

During the Post-Infusion Follow-up Period, each subject will have comprehensive surveillance plan monitoring LFTs once a week from dose to completion of Week 6, 3 times per week from Weeks 7 to 12, and once a week from Weeks 13 to 16. If a subject's ALT is

found to be greater than 1.5x his baseline during these periods, then LFTs will be monitored three times per week until the ALT returns to baseline.

Reports of abnormal LFTs (defined as 1.5x the subject's baseline ALT level) should be made to the BioMarin medical monitor within 30 minutes of the lab value being available, and treatment with prednisolone will be initiated immediately at a dose of 60 mg per day and then gradually tapered (60 mg daily for the first 2 weeks, then 40 mg the next 2 weeks, then 30 mg the next two weeks, then 20 mg the next two weeks, then stop, for a total treatment of 8 weeks). Local laboratory results of LFTs will be used to trigger corticosteroid treatment as needed. In case of discrepant results between local and central laboratories, the Investigator and Medical Monitor will decide further action.

If a glucocorticoid treatment is started for a subject at any point of the study, the following steps will be taken:

- A prophylactic glucocorticoid treatment will be started for subsequent subjects scheduled to be dosed. Subjects will receive prednisolone 40 mg per day starting at week 3, for a duration of 4 weeks, then tapered by 5 mg every two weeks for 8 weeks (until 20 mg/day is reached), then tapered 5 mg per week for 3 weeks, for a total duration of 15 weeks (refer to 4).
 - Subjects already dosed who have not yet reached Week 17 in the study will be evaluated for the use of prophylactic steroids after discussion between the Investigator and the Medical Monitor.
- Once prophylactic glucocorticoid treatments have been initiated, then all subjects (who have not already passed that period in the study) will have 3x/week LFT assessments during the 6-week period when a liver response is expected based on the liver response in the original subject, if this period is different from the 3x/weekly LFT assessments already planned for Weeks 7-12.
 - Subjects who have already passed that 6-week period in the study will continue to have the regularly scheduled LFT assessments as planned in the protocol.
- Management and monitoring of reactions to corticosteroids should be determined by the Investigator's clinical judgment in consultation with the Sponsor's Medical Monitor. This includes the contraindicated use of NSAIDs during corticosteroid treatment, and specific monitoring not already covered by the schedule of events. Hepatitis B status will be rechecked at the end of the corticosteroid treatment. All adverse events should be reported as outlined in Section 10 of the protocol.

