10.2.1 Events of Special Interest (EOSI)

The following EOSI need to be reported to the Sponsor within 24 hours of site awareness, irrespective of seriousness, severity or causality:

• Elevation of liver enzymes (ALT) that triggers a corticosteroid treatment

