10.6 Follow-up of Subjects after Adverse Events

The Investigator should follow all unresolved AEs and SAEs until the events are resolved or have stabilized, the subject is lost to follow-up, or it has been determined that the study treatment or participation is not the cause of the AE/SAE. Resolution of AEs and SAEs (with dates) should be documented on the AE eCRF and submitted to BioMarin Pharmacovigilance and in the subject's medical record to facilitate source data verification.

For some SAEs, the Sponsor may follow up by telephone, fax, electronic mail, and/or a monitoring visit to obtain additional case details (eg, hospital discharge summary, consultant report, or autopsy report) deemed necessary to appropriately evaluate the SAE report.

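### Reactive prednisolone courses begun in Weeks 13-14 end with no scheduled liver test for the next 6-7 weeks

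*Protocol*

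**What the plan says.** All references are to the protocol, Amendment 3 text.

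- **Course.** Section 9.4.8.2 starts prednisolone at once when ALT reaches 1.5 times the subject's baseline: 60 mg, 40 mg and 30 mg for two weeks each, "then 20 mg the next two weeks, then stop, for a total treatment of 8 weeks".
- **Routine LFTs.** The same section sets weekly tests to the end of Week 6, then "3 times per week from Weeks 7 to 12, and once a week from Weeks 13 to 16".
- **Extra LFTs.** A value "found to be greater than 1.5x his baseline during these periods" brings in closer testing with a set end point: "then LFTs will be monitored three times per week until the ALT returns to baseline". The rule is tied to ALT, not to the steroid course.
- **After Week 16.** Sections 12.6 and 12.6.1 schedule blood chemistry, which includes ALT, at Weeks 20, 28, 36, 44 and 52, each ±1 week.
- **Intensive period.** Once prophylaxis is in use, all subjects who have not yet passed the period "will have 3x/week LFT assessments during the 6-week period when a liver response is expected based on the liver response in the original subject".
- **End of course.** The only test tied to the stop is for hepatitis B: "Hepatitis B status will be rechecked at the end of the corticosteroid treatment".

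**The concern.** The taper lasts 8 weeks, but the close LFT surveillance ends at Week 16. A course begun late in that surveillance runs past it and stops at a point when chemistry visits are 8 weeks apart. The weeks just after withdrawal, when a suppressed liver reaction could reappear, may then have no scheduled ALT.

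Safety is the primary endpoint (Section 9.7). Section 9.4.8.2 treats the 1.5-fold threshold as urgent, with a report within 30 minutes and immediate treatment, and the corresponding event is the only one of special interest in Section 10.2.1: "Elevation of liver enzymes (ALT) that triggers a corticosteroid treatment". That trigger can act only when ALT is measured. If ALT rises again off drug, recognition and retreatment would wait for the next visit.

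**Working it through.** **Inputs.** Taper steps of 2 weeks each (9.4.8.2). Scheduled LFT weeks 1 to 16, then 20 and 28, with ±1 week on the last two (9.4.8.2, 12.6, 12.6.1). ALT is taken to be back at baseline, so the three-times-weekly rule has ended.

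**The plan's own figure.** 2 + 2 + 2 + 2 = 8 weeks, which agrees with the stated total.

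**Stop and gap.** Stop week = start week + 8. Gap = next scheduled LFT week − stop week.

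| Start week | Stop week | Next LFT | Gap at nominal times (weeks) | With ±1 week visit window |
|---|---|---|---|---|
| 9 | 17 | 20 | 3 | 2-4 |
| 10 | 18 | 20 | 2 | 1-3 |
| 11 | 19 | 20 | 1 | 0-2 |
| 12 | 20 | 28 | 8 | up to 1 if the Week 20 visit falls after the stop, otherwise 7-9 |
| 13 | 21 | 28 | 7 | 6-8 |
| 14 | 22 | 28 | 6 | 5-7 |
| 15 | 23 | 28 | 5 | 4-6 |
| 16 | 24 | 28 | 4 | 3-5 |

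For a start in Week 12 the nominal Week 20 test coincides with the stop. From Week 16 to Week 28, which is 12 weeks, one LFT is scheduled in between.

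**Edge case.** Weekly visits may move by ±2 days, so the start can too. For Week 14 the shortest gap is 27 − (22 + 2/7) = 4.7 weeks, never within 4. For Week 13 an off-drug test within 4 weeks occurs only if the Week 20 visit is at the very end of its window, on the day of the stop or no more than 2 days after it.

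**Dose at the nominal Week 20 test.** Week 13 start: 20 mg (Weeks 19-21). Week 14 start: the change from 30 to 20 mg. Week 15 start: 30 mg (Weeks 19-21).

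**The 6-week intensive period.** Let it begin in week w and the subject's course in week s. It reaches past the stop only if w + 6 > s + 8, that is w > s + 2. For starts in Weeks 12, 13, 14 and 15 it must begin after Week 14, 15, 16 and 17. If the subject's own start lies inside the period (w ≤ s), the period ends by s + 6, at least 2 weeks before the stop. It therefore cannot help the original subject if it includes his own response.

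**Comparison.** The prophylactic course runs 15 weeks from Week 3 and ends at Week 18, so Week 20 gives an off-drug test 2 weeks later. Under Amendment 2 the reactive taper was 4 weeks, so starts in Weeks 13 and 14 stopped in Weeks 17 and 18 and had the Week 20 test 3 and 2 weeks off drug. The longer taper opened the gap; the visits after Week 16 stayed at the same weeks.

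**The case against.** **The places that fix LFT timing were not all available.** The text at hand is the last of four parts of the protocol file. Amendment 3 Tables 9.1.2 to 9.1.4 are not in it, and later amendments may exist. This stands as a condition on the conclusion. It is weakened by Section 24, whose listed Amendment 3 changes to Tables 9.1.2 and 9.1.3 add no LFTs for reactive courses, and by the title of Table 9.1.4, which concerns prophylaxis.

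**The scenario is narrow.** It needs a trigger at about Weeks 12-15, ALT fully back at baseline and no late intensive period. The expected liver response is at Weeks 7-12, and starts before Week 12 have a test within 4 weeks of the stop at nominal times. Once one subject is treated, later ones receive prophylaxis. All of this stands and limits the size. Weeks 13-14 are nevertheless inside the surveillance that the protocol sets for this trigger.

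**Clinical oversight covers it.** Section 10.6 has investigators "follow all unresolved AEs and SAEs until the events are resolved or have stabilized". Section 9.4.8.2 leaves steroid monitoring to judgment, Section 9.7.8.2 allows repeat tests, Section 15 provides ongoing board review, and the revised synopsis text in Section 24 lets LFT frequency change. Whether a normal ALT under an active taper counts as resolved is a medical judgment. These clauses permit tests and soften the risk, but none fixes an ALT once it is normal.

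**The harm is assumed.** No rate of rise after withdrawal is given, and a Week 20 value on a low dose still carries some information. Both points stand.

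**Conclusion.** The concern holds on the available text. Starts in Weeks 13 and 14 leave 7 and 6 weeks off drug before the next scheduled LFT. Starts in Weeks 12 and 15 also lack a test in the first 4 weeks off drug at nominal visit times, apart from the one at the stop itself for Week 12.

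This is a fixed schedule that fits its own 8-week taper badly. It affects mainly the original subject and others already dosed without prophylaxis; 12 is the ceiling for the whole study, not an estimate. The conclusion assumes that ALT is back at baseline, that the intensive period does not fall late, and that neither the unseen schedule tables nor a later amendment adds tests for reactive courses. The change should be made; confidence is medium because of that last assumption.

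**What to change.** In Sections 9.4.8.2 and 12.6.1, require at least weekly local LFTs for any subject on reactive prednisolone until a fixed time after the last dose, or Week 16 if later. Apply the 1.5-fold trigger and the three-times-weekly rule throughout. Four weeks is a reasonable example of the tail; it is a choice, not a figure from the documents. If the Amendment 3 tables already require this, a cross-reference is enough.

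The cost is two amended sections and some blood draws. Counting weekly tests from Week 17 to stop + 4, less those already due at Weeks 20 and 28:

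- Week 13 start: Weeks 17-25 is 9 tests, less 1 = 8 extra.
- Week 14 start: Weeks 17-26 is 10 tests, less 1 = 9 extra.
- Starts in Weeks 9-16 overall: 4 to 10 extra. Earlier starts: 0 to 3.

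One draw can coincide with the hepatitis B recheck.

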12.5.3 Every 2 Weeks

Every 2 weeks (Weeks 2, 4, 6, 8, 10, 12, 14 and 16), the following procedure will be performed:

• Exploratory biomarker assessments

12.5.4 Weeks 4, 8, 12, and 16

At Weeks 4, 8, 12, and 16, the following procedure will be performed:

• PBMC collection

12.5.5 Weeks 1, 3, and 6

At Weeks 1, 3, and 6, the following procedure will be performed:

• Test for Hepatitis B and Hepatitis C reactivation

12.5.6 Weeks 8 and 16

At Weeks 8 and 16, the following procedure will be performed:

• AAV5 antibody titer

12.5.7 Weeks 1, 2, 3, 4, and 16

At Weeks 1, 2, 3, 4, and 16, the following procedure will be performed:

• Haemo-QoL-A QoL assessment

12.6 Safety Follow-Up – Year 1

After the 16 weekly infusion follow-up visits are complete, subjects will return to the study site at Weeks 20, 28, 36, 44, and 52 (\pm 1 week), when the following procedures will be completed:

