14.2 Primary and Secondary Efficacy Analysis

The subjects will be followed in a longitudinal manner and all the relevant information will be collected. The analysis of the data will be descriptive in nature. Descriptive statistics include the number of subjects, mean, median, standard deviation, minimum, and maximum for continuous variables and count and percent for categorical variables. Efficacy variables will be summarized by dose cohort at each time point. Relationship between dose and efficacy results will be examined.

Data collected in a longitudinal manner may be analyzed using longitudinal methods such as mixed effect model which takes into account the correlation among the observation taken at various time points within a participant. Efficacy is a secondary endpoint, defined as biologically active hFVIII at ≥ 5 IU/dL by chromogenic FXa and/or one-stage APTT assay at 16 weeks following study treatment. hFVIII activity will be assessed weekly during the study period. We can only assess the true steady state of hFVIII protein produced from BMN 270 after a minimum of 72 hours has elapsed since the last infusion of FVIII protein concentrates.

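### If prophylactic prednisolone is triggered, the Week 16 FVIII value of every subject dosed afterwards is an on-steroid value, yet the dose relationship is read by dose cohort alone

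*Protocol*

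**What the plan says.** Protocol Section 9.4.8.2 makes prophylaxis conditional on a first case: "If a glucocorticoid treatment is started for a subject at any point of the study, the following steps will be taken". The first step is: "A prophylactic glucocorticoid treatment will be started for subsequent subjects scheduled to be dosed". The course is fixed: "Subjects will receive prednisolone 40 mg per day starting at week 3, for a duration of 4 weeks". Two tapers come next: one of 8 weeks with a 5 mg reduction each fortnight, and one of 3 weeks with a 5 mg reduction each week. The section gives the total as 15 weeks. Those already treated are handled case by case: "Subjects already dosed who have not yet reached Week 17 in the study will be evaluated for the use of prophylactic steroids". Separately, any subject whose ALT reaches 1.5 times baseline gets an 8-week reactive course.

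Section 9.7 sets the efficacy goal as the dose relationship to FVIII activity of at least 5 IU/dL at 16 weeks. Section 14.2 defines efficacy as reaching that level "by chromogenic FXa and/or one-stage APTT assay at 16 weeks following study treatment" and summarises efficacy variables by dose cohort at each time point. Section 14.1.1 places the primary endpoint analysis after all subjects have completed Week 16. Section 9.7.5 sets the PD window at 0 to 16 weeks. Under Section 9.4.5, cohorts are enrolled serially and escalation uses Week 3 activity. After Week 16, Section 12.6 says "subjects will return to the study site at Weeks 20, 28, 36, 44, and 52", with FVIII measured each time.

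**The concern.** The reading point for the dose question lies inside a co-treatment that the protocol itself imposes, and whether a subject gets that co-treatment depends partly on when he was dosed. In a serially ascending design, dosing order and dose go together. If prophylaxis starts partway through the trial, a higher Week 16 level in a later cohort could reflect dose, steroid or both, and the by-cohort summary cannot tell them apart. If it starts midway through a cohort, that cohort's summary mixes on-steroid and off-steroid values.

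An effect of the steroid on the reading is plausible on the protocol's own terms. Section 9.4.8 prohibits systemic immunosuppressive agents from 30 days before Screening. Section 9.7.4 compares antibody rises with FVIII activity and sends liver abnormalities to T-cell assessment against capsid and FVIII. At stake is the statement of which dose achieves 5 IU/dL.

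**Working it through.** **Inputs.** Prophylactic and reactive courses: Section 9.4.8.2. Visit windows: ±48 hours to Week 16 (Section 12.5), ±1 week for Weeks 20 to 52 (Section 12.6). Spacing of at least 3 weeks between subjects: Section 9.4.6.1. Table 9.1.4, which holds the steroid schedule, is not in the text available.

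**1. The plan's own figure.** 4 weeks at 40 mg, four 2-week steps (35, 30, 25, 20 mg) and three 1-week steps (15, 10, 5 mg): 4 + 8 + 3 = 15 weeks. This reproduces the stated total.

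**2. The course on the study calendar.** Week 3 can mean 3 completed weeks after infusion or the start of the third week (2 completed weeks). Week 16 ±48 hours is 15.71 to 16.29 weeks.

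| Start (completed weeks) | End | Scheduled dose in the Week 16 window |
|---|---|---|
| 3 | 3 + 15 = 18 | 15 mg before week 16, 10 mg from week 16 |
| 2 | 2 + 15 = 17 | 10 mg before week 16, 5 mg from week 16 |

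The whole Week 16 window lies inside the course on both readings.

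**3. Share of the PD window.** 16 − 3 = 13 weeks (13/16 = 81%) or 16 − 2 = 14 weeks (14/16 = 88%) on steroid.

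**4. Reactive course.** End = trigger week + 8. A trigger at Week 8 ends at Week 16, and any later trigger covers Week 16. Triggers at Weeks 9 to 12, within the intensive monitoring period of Weeks 7 to 12, end at Weeks 17 to 20.

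**5. First value after the course.** For the fixed course this is Week 20, which is 2 to 3 weeks after the end (20 − 18, 20 − 17). Allowing for the visit window, the earliest is 19 weeks, still after the end. Week 28 is 10 to 11 weeks after the end. A reactive course triggered at Week 12 ends at Week 20, so its first visit clearly afterwards is Week 28.

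**6. Link with dosing order.** It depends on the timing of the first trigger.
- No trigger: no prophylaxis and no confounding.
- Early trigger with fastest escalation: subjects 1, 2 and 3, one per dose, are infused at calendar weeks 0, 3 and 6. If subject 1 triggers at Weeks 7 to 12, subject 2 is at Weeks 4 to 9 and subject 3 at Weeks 1 to 6. All are before Week 17, so all would be evaluated for prophylaxis.
- Later trigger, after the low-dose subjects have passed Week 17: the fixed course goes only to those still to be dosed, who with upward dosing tend to be at the higher doses.
- Trigger midway through a cohort: subjects at the same dose differ in exposure.

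Under Section 9.4.6.2, Cohort 1 or 2 stops at one subject if that subject does not reach 5 IU/dL in both assays. With at most 12 subjects (Section 14.6), little may be left for separating dose from steroid.

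**The case against.** Several objections stand and limit the point.

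- **Who is exposed.** A reader might infer that only later-dosed subjects receive steroids. Section 9.4.8.2 says otherwise: subjects already dosed and before Week 17 may be given prophylaxis, with start and length not stated, and anyone may receive the reactive course.
- **Stability.** A reader might infer that stable expression is also judged at Week 16. Section 9.7.2 does not tie it to that visit. It describes regular monitoring and points to the safety follow-up schedule.
- **Mechanism.** That prednisolone is given to preserve FVIII expression is not stated. Section 9.4.8.2 concerns elevated transaminases.
- **Escalation.** It uses Week 3 activity, when the fixed course is at most just beginning.
- **Later visits.** Section 14.2 already promises summaries by cohort at each time point, so post-course values by cohort are planned output.
- **SAP.** A breakdown by concomitant medication could sit in the SAP, which is not at hand.

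The last two do not remove the point. The protocol itself fixes Week 16 and the dose-cohort contrast as the efficacy reading, without recognising that its own mandated course spans that visit. When the primary analysis is run after the last Week 16 visit, the last-dosed subjects may have no value from after the course. Later summaries by cohort alone would still pool different steroid histories.

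**Conclusion.** The point holds conditionally. If prophylaxis is triggered, every subject on the fixed course from week 3 is on prednisolone at Week 16, and 13 to 14 of the 16 weeks of the PD window are on steroid. This follows from the protocol's own figures under either reading of week 3. Steroid exposure may then be partly aliased with dose, or split within a cohort. How far cannot be computed in advance, because it depends on when the first trigger occurs and on enrolment speed.

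The documents do not support saying that dose and steroid are confounded in any event, that steroids raise Week 16 activity by some amount, or that durability cannot be assessed. The planned analysis is descriptive and unpowered, so no error rate or power is affected. This is a badly fixed reading point with a cheap remedy. It rests on the Amendment 3 text shown; other parts of the document and the SAP have not been seen.

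**What to change.** Keep Week 16 as planned and amend Section 14.2 to:

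1. Present FVIII activity and the count at or above 5 IU/dL by dose and steroid exposure (none, reactive, prophylactic), marking whether the subject was on or off steroid at the visit.
2. Report beside Week 16 the value at the first scheduled visit after the steroid course has ended (Week 20 for the fixed course, with Week 28 as a supporting value). Base the statement on the dose that sustains 5 IU/dL on both.
3. State that dose contrasts between subjects with different steroid exposure cannot be attributed to dose alone.

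The cost is analysis wording and one tabulation, using existing visits and the concomitant medication records already required by Section 9.4.8. With so few subjects, cells will be small and individual listings should accompany the table. For the last-dosed subjects on the fixed course, the off-steroid statement comes 4 weeks (20 − 16) to 12 weeks (28 − 16) after their Week 16 visit. No change to steroid treatment is proposed.

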9.4.9 Treatment Compliance

Study drug will be administered to subjects at the study site by a qualified professional. The quantity dispensed, returned, used, lost, etc. must be recorded on the dispensing log provided for the study. Sites will be instructed to return or destroy all used and unused study drug containers.

9.5 Investigational Product Accountability

The Investigator or designee is responsible for maintaining accurate records (including dates and quantities) of IP(s) received and IP lost or accidentally or deliberately destroyed. The Investigator or designee must retain all unused or expired study supplies until the study monitor (on-site CRA) has confirmed the accountability data.

9.5.1 Return and Disposition of Clinical Supplies

Unused study drug must be kept in a secure location for accountability and reconciliation by the study monitor. The Investigator or designee must provide an explanation for any destroyed or missing study drug or study materials.

Unused study drug may be destroyed on site, per the site's standard operating procedures, but only after BioMarin has granted approval for drug destruction. The monitor must account for all study drug in a formal reconciliation process prior to study drug destruction. All study drug destroyed on site must be documented. Documentation must be provided to BioMarin and retained in the Investigator study files. If a site is unable to destroy study drug appropriately, the site can return unused study drug to BioMarin upon request. The return of study drug or study drug materials must be accounted for on a Study Drug Return Form provided by BioMarin.

All study drug and related materials should be stored, inventoried, reconciled, and destroyed or returned according to applicable state and federal regulations and study procedures.

